10.3.4 Exploratory analysis

Exploratory biomarker analyses will be performed in order to understand the association of these markers with study drug response, including efficacy and/or adverse events.

Exploratory biomarker analyses will include assessments of biomarkers in both tumor tissue and blood. Changes in biomarkers will be listed by cohort and response status. The pharmacodynamic biomarker analyses will include patients with at least one predose and one postdose biomarker assessment.

11.0 LABELING, PACKAGING, STORAGE AND RETURN OF CLINICAL SUPPLIES

11.1 Investigational Product

The investigator shall take responsibility for and shall take all steps to maintain appropriate records and ensure appropriate supply, storage, handling, distribution and usage of investigational product in accordance with the protocol and any applicable laws and regulations.

Pembrolizumab will be provided by Merck and Temozolomide by the Sponsor through Niguarda Pharmacy, as summarized in Table 11.

Table 11. Product Descriptions

Product Name & Potency	Dosage Form
Pembrolizumab 100 mg/ 4mL	Solution for Injection
Temozolomide 5, 20, 100, 250 mg	Hard Capsules

11.2 Packaging and Labeling Information

Supplies will be labeled in accordance with regulatory requirements. Pembrolizumab will be labelled as MK-3475.

11.3 Clinical Supplies Disclosure

This trial is open-label; therefore, the participant, the trial site personnel, the Sponsor and/or designee are not blinded to treatment. Drug identity (name, strength) is included in the label text; random code/disclosure envelopes or lists are not provided.

11.4 Storage and Handling Requirements

Clinical supplies must be stored in a secure, limited-access location under the storage conditions specified on the label.

Receipt and dispensing of trial medication must be recorded by an authorized person at the trial site.

Clinical supplies may not be used for any purpose other than that stated in the protocol.

11.5 Returns and Reconciliation

The investigator is responsible for keeping accurate records of the clinical supplies received from Merck or designee, the amount dispensed to and returned by the participants and the amount remaining at the conclusion of the trial.

Upon completion or termination of the study, all unused and/or partially used investigational product will be destroyed at the site per institutional policy. It is the Investigator's responsibility to arrange for disposal of all empty containers, provided that procedures for proper disposal have been established according to applicable federal, state, local and institutional guidelines and procedures, and provided that appropriate records of disposal are kept.

12.0 ADMINISTRATIVE AND REGULATORY DETAILS

12.1 Confidentiality

Sponsor assures that the key design element of this protocol will be posted in a publicly accessible database such as EUDRACT and clinicaltrial.gov; in addition, upon study

completion, the results of this study will be submitted for publication and posted in publicly accessible database for clinical trial studies.

All information regarding study drug supplied by Sponsor to the investigator is privileged and confidential information. The investigator agrees to use this information to accomplish the study and will not use it for other purposes without consent from Sponsor.

It is understood that there is an obligation to provide Sponsor with complete data obtained during the study. The investigator agrees to keep in confidence all the results obtained from the study. Such information shall not be disclosed to third parties without prior written permission from Sponsor, except to regulatory authority(ies), when requested.

Individual investigators may present results of the study at scientific meetings. However prior to the submission, the Sponsor will have the opportunity to review and comment the abstracts for a period of up to 15 calendar days prior to the submission.

12.2 Data Management

Data Management will be carried out by a delegated CRO. Medical terms are coded according to the MedDRA dictionary. Data will be analyzed using SAS® System currently used at CRO. Data cleaning will include both visual and computer-driven procedures in order to minimize logical inconsistencies and errors within the collected data. The data are checked for completeness, accuracy and consistency. The errors detected will be rectified by means of Data Clarification List (DCL) that will be used by the monitor for resolution of queries.

12.2.1 Record Retention

To enable evaluation and/or audits and/or regulatory authorities inspections, the Investigator agrees to keep records, including the identity of all participating subjects (“Subject identification Log”), all original signed informed consent forms, copies of all case report forms, source documents, detailed records of treatment disposition as well as the documentation included in the Investigator File according to local regulations or as specified in the Clinical Trial Agreement.

If the Investigator relocates, retires, or for any reason withdraws from the study, Sponsor should be prospectively notified. The study records must be transferred to an acceptable designee, such as another investigator, another institution, or to delegated CRO. The investigator must obtain Sponsor’s written permission before disposing of any records.

Appendix 1: ECOG Performance Status

Grade	Description
0	Normal activity. Fully active, able to carry on all pre-disease performance without restriction.
1	Symptoms, but ambulatory. Restricted in physically strenuous activity, but ambulatory and able to carry out work of a light or sedentary nature (e.g., light housework, office work).
2	In bed <50% of the time. Ambulatory and capable of all self-care, but unable to carry out any work activities. Up and about more than 50% of waking hours.
3	In bed >50% of the time. Capable of only limited self-care, confined to bed or chair more than 50% of waking hours.
4	100% bedridden. Completely disabled. Cannot carry on any self-care. Totally confined to bed or chair.
5	Dead.
* As published in Am. J. Clin. Oncol.: Oken, M.M., Creech, R.H., Tormey, D.C., Horton, J., Davis, T.E., McFadden, E.T., Carbone, P.P.: Toxicity And Response Criteria Of The Eastern Cooperative Oncology Group. Am J Clin Oncol 5:649-655, 1982. The Eastern Cooperative Oncology Group, Robert Comis M.D., Group Chair.	

Appendix 2: Common Terminology Criteria for Adverse Events V4.03 (CTCAE)

The descriptions and grading scales found in the revised NCI Common Terminology Criteria for Adverse Events (CTCAE) version 4.03 will be utilized for adverse event reporting. (https://evs.nci.nih.gov/ftp1/CTCAE/CTCAE_4.03/CTCAE_4.03_2010-06-14_QuickReference_5x7.pdf)

Appendix 3: Contraception Requirements

Female Participants:

Female participants of childbearing potential are eligible to participate if they agree to use one of the contraception methods described in Table A3 consistently and correctly during the protocol-defined time frame in section 8.0 and 9.0.

Table A3: Contraceptive Methods

Acceptable Contraceptive Methods
Failure rate of >1% per year when used consistently and correctly.

 ● Male or female condom with or without spermicide ● Cervical cap, diaphragm or sponge with spermicide

Highly Effective Contraceptive Methods That Are User Dependent ^a
 
Failure rate of <1% per year when used consistently and correctly.
 
 ● Combined (estrogen- and progestogen- containing) hormonal contraception ^b 
 ○ Oral ○ Intravaginal ○ Transdermal ○ Injectable ● Progestogen-only hormonal contraception ^b 
 ○ Oral ○ Injectable

Highly Effective Methods That Have Low User Dependency
 
Failure rate of <1% per year when used consistently and correctly.
 
 ● Progestogen- only contraceptive implant ^{b, c} ● Intrauterine hormone-releasing system (IUS) ^b ● Intrauterine device (IUD) ● Bilateral tubal occlusion

 ● Vasectomized partner A vasectomized partner is a highly effective contraception method provided that the partner is the sole male sexual partner of the WOCBP and the absence of sperm has been confirmed. If not, an additional highly effective method of contraception should be used. ● Sexual abstinence Sexual abstinence is considered a highly effective method only if defined as refraining from heterosexual intercourse during the entire period of risk associated with the study treatment. The reliability of sexual abstinence needs to be evaluated in relation to the duration of the study and the preferred and usual lifestyle of the participant.)

Notes:
 
Use should be consistent with local regulations regarding the use of contraceptive methods for participants of clinical studies.
 
a) Typical use failure rates are lower than perfect-use failure rates (i.e. when used consistently and correctly).
 
b) If hormonal contraception efficacy is potentially decreased due to interaction with study treatment, condoms must be used in addition to the hormonal contraception during the treatment period and for at least 60 days after the last dose of study treatment .
 
c) If locally required, in accordance with Clinical Trial Facilitation Group (CTFG) guidelines, acceptable hormonal contraceptives are limited to those which inhibit ovulation.

Pregnancy Testing: WOCBP should only be included after a negative highly sensitive urine or serum pregnancy test.

Pregnancy testing will be performed whenever an expected menstrual cycle is missed or when pregnancy is otherwise suspected.

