7.1.2 Entry Criteria for PRIMING Phase

Participants are eligible to be included in the PRIMING Phase, only if all of the following criteria apply:

1. Fulfilment of all the SCREENING inclusion criteria;
2. PRIMING informed consent signed;
3. Confirming the willingness to undergo two tumor biopsies,
4. Acceptance that if the mutational load determination is unfeasible for technical reasons (not enough tissue, substandard test performance, etc.), access to TRIAL phase will not be possible.
5. Imaging documented failure of previous standard CRC therapies including fluoropyrimidine, oxaliplatin, irinotecan plus or minus antiangiogenics agents (Bevacizumab, Aflibercept, Regorafenib, others).
6. At least one measurable tumor lesion as per RECIST v1.1. Lesions in previously irradiated areas or those that have received other loco-regional therapies (i.e. percutaneous ablation) should not be considered measurable unless there is clear documented evidence of progression of the lesion since therapy. Imaging must be performed maximum within 28 days prior to enrolment.
7. ECOG performance status 0 or 1;
8. Following results in the SCREENING Phase tests:
 - Proficient MMR status assessed by IHC or MSI-low status defined by PCR (Bethesda panel);
 - Negative score for the MGMT protein expression IHC test;
 - Positive score for the MGMT promoter methylation performed on tissue.
9. Women with childbearing potential should complete a pregnancy test and be willing to use highly effective contraceptive methods.
10. Normal organ functions as defined in the Table 7.1.4 below.

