7.1.3 Entry Criteria for TRIAL Phase

1. Fulfilment of all the SCREENING inclusion criteria and deficient MMR status (IHC) or MSI-High status (PCR) (cohort D only).
2. Fulfilment of all the SCREENING and PRIMING inclusion criteria (cohort P only).
3. TRIAL Phase informed consent signed (both cohorts).
4. Imaging documented PD to TMZ (cohort P only).
5. A mutational load value ≥ 20 mutations/MB at TMZ-ML assay (cohort P only).
6. Imaging documented failure of previous standard CRC therapies including fluoropyrimidine, oxaliplatin, irinotecan plus or minus targeted agents (Bevacizumab, Aflibercept, Regorafenib, Cetuximab, Panitumumab, others) (cohort D only).
7. At least one measurable tumor lesion as per RECIST v1.1. Lesions in previously irradiated areas or those that have received other loco-regional therapies (i.e. percutaneous ablation) should not be considered measurable unless there is clear documented evidence of progression of the lesion since therapy. Imaging must be performed maximum within 28 days prior to enrolment (both cohorts).
8. Women with childbearing potential should complete a pregnancy test and be willing to use highly effective contraceptive methods (both cohorts).
9. Normal organ functions as defined in the Table 7.1.4 below. Blood specimens must be collected within 10 days prior to the start of study treatment.

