7.2.1.2 Contraception

ICH M3 guidance requires precautions to be taken to minimize risk to fetus or embryo when including women of childbearing potential in clinical studies.

Temozolomide and Pembrolizumab may have adverse effects on a fetus in utero. Refer to Appendix 3 for approved methods of contraception.

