10.3 Statistical Analysis Plan

10.3.1 Populations considered for the analysis

All patients signing the informed consent for the PRIMING and TRIAL Phases will be accounted for. The number of patients who will not result eligible, who died or withdrew before these phases, will be specified.

A patient will be considered to be PRIMING and TRIAL Phases eligible if he/she did not have any deviation from the patient entry criteria listed in section 7.1.2 (PRIMING) and 7.1.3 (TRIAL). Potential eligibility problems will be assessed by the Clinical Study Coordinator at time of medical review.

The final efficacy analysis will occur after 20 patients entered in the P-Cohort are evaluable for response according to RECIST 1.1. The distribution of follow-up time in both cohorts (P and D) will be described and the number of patients lost to follow-up will be reported.

Conclusions will be based on all eligible patients in each cohort. Further analysis may be performed excluding those patients for whom major protocol deviations have been identified (e.g., early death due to other reasons, early discontinuation of treatment, major protocol violations, etc.). However, these sub-analyses may not serve as the basis for drawing conclusions concerning treatment efficacy, and the reasons for excluding patients from the analysis should be clearly reported.

Three populations will be considered for the analysis, as follows:

- The Safety Evaluable (SE) population defined as all treated patients (i.e. eligible as decided at the time of registration that receives at least 1 dose of any study treatment i.e. TMZ and Pembrolizumab). An incorrect treatment schedule or drug administration or an early termination of treatment does not result in exclusion of patients from this population. This population will be the object of the Safety and Tolerability analysis. Patients with major deviations from the eligibility criteria affecting safety or from the treatment schedule at cycle 1 for reasons other than toxicity may be presented in separate tables/listings.
- The Efficacy Evaluable (EE) population defined as all patient treated with pembrolizumab in P-cohort, with no major deviations from the eligibility criteria affecting efficacy evaluation, for which the tumor response could be evaluated at least once while on treatment. These patients should have received at least 2 cycles after treatment starts, unless disease progression occurs within this period.

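### Appendix 3 makes a woman eligible on a barrier method alone, although PRIMING criterion 9 and TRIAL criterion 8 require highly effective contraception

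*Combined protocol and SAP*

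**What the plan says.** The entry criteria set one standard. Section 7.1.2 opens with "Participants are eligible to be included in the PRIMING Phase, only if all of the following criteria apply", and its criterion 9 reads "Women with childbearing potential should complete a pregnancy test and be willing to use highly effective contraceptive methods". Section 7.1.3 criterion 8 repeats the requirement for both cohorts, and the synopsis carries it for both phases.

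Section 7.2.1.2 warns: "Temozolomide and Pembrolizumab may have adverse effects on a fetus in utero". It then directs the site elsewhere for the detail: "Refer to Appendix 3 for approved methods of contraception".

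Appendix 3 sets a different standard: "Female participants of childbearing potential are eligible to participate if they agree to use one of the contraception methods described in Table A3". Table A3 has three tiers:

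- The first, headed as acceptable, has a stated failure rate above 1% per year. It contains "Male or female condom with or without spermicide" and the cap, diaphragm or sponge with spermicide.
- The second and third are headed as highly effective, with stated failure rates below 1% per year.

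**The concern.** The protocol's own tier headings mark the barrier methods as not highly effective. Even so, the Appendix 3 sentence accepts any single method from the table as sufficient for eligibility. This is an operative rule in the place to which sites are sent, and it gives a different answer from the numbered entry criteria.

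What is at stake is fetal safety. Treatment can be long: temozolomide is given until progression and pembrolizumab for up to 24 months, with a possible second course of about a year (section 7.3.5). The flow chart in section 8.0 schedules serum pregnancy tests only at the first temozolomide cycle and the first pembrolizumab cycle. After that, Appendix 3 asks for a test only when a menstrual cycle is missed or pregnancy is suspected. Contraception is the continuing protection between those points.

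A secondary consequence concerns data quality. Section 10.3.1 defines PRIMING and TRIAL eligibility as having no deviation from the criteria in 7.1.2 and 7.1.3. A woman admitted under Appendix 3 on a barrier method alone would be an eligibility deviation caused by the protocol's own text.

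**Working it through.** The plan gives no figure to reproduce. The check compares the texts and then makes a simple count.

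**1. The rules side by side, for a woman whose only method is a condom**

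| Place | Standard | Result |
|---|---|---|
| 7.1.2 criterion 9 (PRIMING) | Highly effective method | Not eligible |
| 7.1.3 criterion 8 (TRIAL, both cohorts) | Highly effective method | Not eligible |
| Appendix 3, opening sentence | Any one Table A3 method | Requirement met |

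**2. Does a note to Table A3 remove the conflict?** Four notes were checked.

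- The general note asks for consistency with local regulations. It sets no contraceptive standard.
- Note a concerns typical-use and perfect-use failure rates.
- Note b adds a condom to a hormonal method when an interaction with study treatment is possible. It does not address a barrier method used alone.
- Note c limits hormonal methods where local rules require it.

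None restricts the first tier to use alongside another method.

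**3. Which text should give way?** The PRIMING criteria must all be met. Section 7.1.3 criterion 2 carries them forward for cohort P, and 7.1.3 criterion 8 applies directly to both cohorts. Section 10.3.1 ties eligibility to 7.1.2 and 7.1.3 and does not name Appendix 3. The stricter standard also fits the warning in 7.2.1.2. The sentence to correct is the one in Appendix 3.

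**4. Count of Table A3 entries**

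- Acceptable tier: condom; cap, diaphragm or sponge = 2
- Highly effective, user dependent: combined hormonal; progestogen-only = 2
- Highly effective, low user dependency: implant; hormone-releasing intrauterine system; intrauterine device; tubal occlusion = 4
- Vasectomized partner = 1; abstinence = 1

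Total: 2 + 2 + 4 + 1 + 1 = 10. Below the entry-criteria standard: 2 of 10.

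**5. Possible reach.** Planned treated patients are 67 in PRIMING plus up to 34 in cohort D: 67 + 34 = 101. The 20 cohort P patients are already among the 67. The documents give no share of women of childbearing potential or of barrier-only users. With an assumed barrier-only share of 1% to 5% of all planned treated patients:

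- 0.01 × 101 = 1.01
- 0.05 × 101 = 5.05

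That is about 1 to 5 patients.

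**6. Effect on the analysis.** The efficacy evaluable population in 10.3.1 excludes only major eligibility deviations that bear on efficacy evaluation, and a contraceptive method does not. The safety population takes eligibility as judged at registration and requires one dose of study treatment, so she would remain in it. The two-stage design in 10.2 uses none of these texts.

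**The case against.** The strongest reply is that the entry criteria already settle the matter. The highly effective standard appears four times, twice in the synopsis and once each in 7.1.2 and 7.1.3. Section 9.1.1.2 has the investigator review every criterion, and Table A3 labels its tiers, so a site checking criterion 9 or 8 can see which rows qualify. Harm requires a site to apply Appendix 3 and pass over a numbered criterion. Other safeguards exist: a negative pregnancy test before inclusion, exclusion of a positive serum test within 72 hours, exclusion of anyone expecting to conceive up to 120 days after the last dose, and immediate discontinuation on pregnancy. The protocol also states no order of precedence between body and appendix, and the lead-in requiring all criteria appears in 7.1.2 but not in 7.1.3.

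Part of this stands. A careful reader would apply the stricter rule, so few patients are likely to be affected. The figure of 101 includes men and women not of childbearing potential. It is also a planned number, not a strict limit on exposure, because sections 7.8.1 and 7.8.2 replace some patients who may already have been treated. The 1% to 5% share has no source in the documents.

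The conflict remains. If the entry criteria prevail, the Appendix 3 sentence is wrong. If nothing prevails, sites hold two contradictory eligibility rules, one of them in the place named for approved methods. Pregnancy tests and the exclusion of women expecting to conceive reduce the risk, but they set no standard for the contraceptive method.

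**Conclusion.** The concern holds. The eligibility sentence in Appendix 3 is wrong as written against section 7.1.2 criterion 9 and section 7.1.3 criterion 8. This rests on the text alone and needs no outside standard, because Table A3 itself separates methods above and below 1% failure per year.

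The reach is small. It is confined to women of childbearing potential who would rely solely on a barrier method, at a site that applies Appendix 3 without the entry criteria. The range of about 1 to 5 patients depends entirely on the assumed share, and the conclusion does not depend on it.

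This is a participant-safety correction with no effect on sample size or error rates and no plausible effect on the primary analysis. It should be made because the possible harm is serious and the correction is easy.

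**What to change.** Leave criterion 9 of 7.1.2 and criterion 8 of 7.1.3 unchanged and let them prevail. Reword the Appendix 3 sentence so that a woman of childbearing potential must agree to use one of the highly effective methods in Table A3, counting a vasectomized partner and abstinence under the conditions already stated there. Then either delete the tier with failure above 1% per year, or relabel it as methods allowed only in addition to a highly effective one. Note b, on adding condoms to hormonal methods, can stay.

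The cost is one clause in Appendix 3 and the deletion or relabelling of one tier of the table. Design, sample size and analysis do not change.

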Appendix 4: Response assessment criteria

Response Evaluation Criteria in Solid Tumors (RECIST) 1.1

RECIST version 1.1* will be used in this study for assessment of tumor response. While either CT or MRI may be utilized, as per RECIST 1.1, CT is the preferred imaging technique in this study.

* As published in the European Journal of Cancer:

E.A. Eisenhauer, P. Therasse, J. Bogaerts, L.H. Schwartz, D. Sargent, R. Ford, J. Dancey, S. Arbuck, S. Gwyther, M. Mooney, L. Rubinstein, L. Shankar, L. Dodd, R. Kaplan, D. Lacombe, J. Verweij. New response evaluation criteria in solid tumors: Revised RECIST guideline (version 1.1). Eur J Cancer. 2009 Jan;45(2):228-47.

In addition, volumetric analysis will be explored by central review for response assessment.

Immune Response Evaluation Criteria in Solid Tumors (iRECIST) Criteria for Evaluating Response in Solid Tumors

iRECIST will be used in this study for assessment of tumor response. While either CT or MRI may be utilized, as per iRECIST, CT is the preferred imaging technique in this study.

In addition, volumetric analysis will be explored by central review for response assessment.

Assessment at Screening and Prior to RECIST 1.1 Progression

Until radiographic progression based on RECIST 1.1, there is no distinct iRECIST assessment.

Assessment and Decision at RECIST 1.1 Progression

In participants who show evidence of radiological PD by RECIST 1.1 the Investigator will decide whether to continue a participant on study treatment until repeat imaging is obtained. This decision by the Investigator should be based on the participant's overall clinical condition.

Clinical stability is defined as the following:

- Absence of symptoms and signs indicating clinically significant progression of disease
- No decline in ECOG performance status
- No requirements for intensified management, including increased analgesia, radiation, or other palliative care

Any participant deemed clinically unstable should be discontinued from study treatment at site-assessed first radiologic evidence of PD, and is not required to have repeat tumor imaging for confirmation of PD by iRECIST.

If the Investigator decides to continue treatment, the participant may continue to receive study treatment and the tumor assessment should be repeated 4 to 8 weeks later to confirm PD by iRECIST, per Investigator assessment. I

Tumor flare may manifest as any factor causing radiographic progression per RECIST 1.1, including:

- Increase in the sum of diameters of target lesion(s) identified at baseline to $\geq 20\%$ and ≥ 5 mm from nadir
 - Please note: the iRECIST publication uses the terminology “sum of measurements”, but “sum of diameters” will be used in this protocol, consistent with the original RECIST 1.1 terminology.
- Unequivocal progression of non-target lesion(s) identified at baseline
- Development of new lesion(s)

iRECIST defines new response categories, including iUPD (unconfirmed progressive disease) and iCPD (confirmed progressive disease). For purposes of iRECIST assessment, the first visit showing progression according to RECIST 1.1 will be assigned a visit (overall) response of iUPD, regardless of which factors caused the progression.

At this visit, target and non-target lesions identified at baseline by RECIST 1.1 will be assessed as usual.

New lesions will be classified as measurable or non-measurable, using the same size thresholds and rules as for baseline lesion assessment in RECIST 1.1. From measurable new lesions, up to 5 lesions total (up to 2 per organ), may be selected as New Lesions – Target. The sum of diameters of these lesions will be calculated, and kept distinct from the sum of diameters for target lesions at baseline. All other new lesions will be followed qualitatively as New Lesions – Non-target.

Assessment at the Confirmatory Imaging

On the confirmatory imaging, the participant will be classified as progression confirmed (with an overall response of iCPD), or as showing persistent unconfirmed progression (with an overall response of iUPD), or as showing disease stability or response (iSD/iPR/iCR).

Confirmation of Progression

Progression is considered confirmed, and the overall response will be iCPD, if ANY of the following occurs:

- Any of the factors that were the basis for the initial iUPD show worsening
 - For target lesions, worsening is a further increase in the sum of diameters of ≥ 5 mm, compared to any prior iUPD time point
 - For non-target lesions, worsening is any significant growth in lesions overall, compared to a prior iUPD time point; this does not have to meet the “unequivocal” standard of RECIST 1.1
 - For new lesions, worsening is any of these:
 - An increase in the new lesion sum of diameters by ≥ 5 mm from a prior iUPD time point
 - Visible growth of new non-target lesions
 - The appearance of additional new lesions
- Any new factor appears that would have triggered PD by RECIST 1.1

Persistent iUPD

Progression is considered not confirmed, and the overall response remains iUPD, if:

- None of the progression-confirming factors identified above occurs AND
- The target lesion sum of diameters (initial target lesions) remains above the initial PD threshold (by RECIST 1.1)

Additional imaging for confirmation should be scheduled 4 to 8 weeks from the scan on which iUPD is seen. This may correspond to the next visit in the original visit schedule. The assessment of the subsequent confirmation scan proceeds in an identical manner, with possible outcomes of iCPD, iUPD, and iSD/iPR/iCR.

Resolution of iUPD

Progression is considered not confirmed, and the overall response becomes iSD/iPR/iCR, if:

- None of the progression-confirming factors identified above occurs, AND
- The target lesion sum of diameters (initial target lesions) is not above the initial PD threshold.

The response is classified as iSD or iPR (depending on the sum of diameters of the target lesions), or iCR if all lesions resolve.

In this case, the initial iUPD is considered to be pseudo-progression, and the level of suspicion for progression is “reset”. This means that the next visit that shows radiographic progression, whenever it occurs, is again classified as iUPD by iRECIST, and the confirmation process is repeated before a response of iCPD can be assigned.

Management Following the Confirmatory Imaging

If repeat imaging does not confirm PD per iRECIST, as assessed by the Investigator, and the participant continues to be clinically stable, study treatment may continue and follow the regular imaging schedule. If PD is confirmed, participants will be discontinued from study treatment.

NOTE: If a participant has confirmed radiographic progression (iCPD) as defined above, but the participant is achieving a clinically meaningful benefit, an exception to continue study treatment may be considered. In this case, if study treatment is continued, tumor imaging should continue to be performed following the intervals as outlined in section 8.0.

Detection of Progression at Visits After Pseudo-progression Resolves

After resolution of pseudo-progression (ie, achievement of iSD/iPR/iCR), iUPD is indicated by any of the following events:

- Target lesions
 - Sum of diameters reaches the PD threshold ($\geq 20\%$ and ≥ 5 mm increase from nadir) either for the first time, or after resolution of previous pseudo-progression. The nadir is always the smallest sum of diameters seen during the entire trial, either before or after an instance of pseudo-progression.
- Non-target lesions
 - If non-target lesions have never shown unequivocal progression, their doing so for the first time results in iUPD.
 - If non-target lesions had shown previous unequivocal progression, and this progression has not resolved, iUPD results from any significant further growth of non-target lesions, taken as a whole.
- New lesions
 - New lesions appear for the first time
 - Additional new lesions appear
 - Previously identified new target lesions show an increase of ≥ 5 mm in the new lesion sum of diameters, from the nadir value of that sum
 - Previously identified non-target lesions show any significant growth

If any of the events above occur, the overall response for that visit is iUPD, and the iUPD evaluation process (see Assessment at the Confirmatory Imaging above) is repeated. Progression must be confirmed before iCPD can occur.

The decision process is identical to the iUPD confirmation process for the initial PD, except in one respect. If new lesions occurred at a prior instance of iUPD, and at the confirmatory scan the burden of new lesions has increased from its smallest value (for new target lesions, their sum of diameters is ≥ 5 mm increased from its nadir), then iUPD cannot resolve to iSD or iPR. It will remain iUPD until either a decrease in the new lesion burden allows resolution to iSD or iPR, or until a confirmatory factor causes iCPD.

Additional details about iRECIST are provided in the iRECIST publication (Seymour et al., 2017).

